12.5. Discontinuation of Treatment and Withdrawal of Patients

Patients may withdraw informed consent and discontinue from the study at any time, or for any reason, without prejudice to their future treatment. In addition, a patient must be discontinued from the study if any of the following criteria are met:

- Significant patient non-compliance with the protocol, as agreed by the investigator and the sponsor
- Patient lost to follow-up
- Termination of the study by the sponsor
- Patient experiences an unacceptable toxicity that precludes them from continuing in the study e.g. patient experiences a ventricular arrhythmia (see Section 12.2.1), as agreed by the investigator and the sponsor
- Lack of adequate recovery from a first cycle DLT, see Section 9.2.1.2
- Failure of toxicity to adequately resolve, as outlined in Table 7
- Female patient becomes pregnant

- Patient experiences PD (unless in the opinion of the investigator, they continue to derive clinical benefit and are permitted to continue on study after discussion and agreement between investigator, the patient and Sponsor. All decisions will be documented in writing).

Note: Clinical benefit in this context is defined as meeting one or several of the following criteria: evidence of disease stabilization after documented initial progression (patient is stably worse), tolerance of drug(s), absence of rapid progression based on peripheral or bone marrow blasts and clinical hematology and clinical chemistry parameters, maintenance of good performance status (PS of 2 or less and not deteriorating], absence of worsening clinical symptoms (i.e., no symptomatic deterioration) and/or improvements in patient's quality of life). This will not affect the time point of disease progression from the perspective of trial analysis.

- Patient and/or investigator decide that it is in the patient's best interest to withdraw from study treatment or the patient withdraws consent

AEs resulting in discontinuation will be followed as outlined in Section 9.3.4.

Patients who discontinue during the DLT assessment period (Part A), for any reason other than a DLT, will be replaced. All other patients who discontinue study treatment will not be replaced.

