Progressive Disease ^c	PD	>50% increase in myeloblasts over the pretreatment value (a minimum 15% increase is required if <30% myeloblasts pretreatment)	>50% increase in PB to $>25 \times 10^9/L$ or $>25,000/\mu L$ ^d			New EMD disease

a. PBs are quantified as an automated WBC times percentage of blasts by manual differential (100 cells) per standard clinical laboratory procedures.
 b. BM examination should not be aplastic, and have at least 200 cells or cellularity should be at least 10%
 c. PD is usually accompanied by a decline in ANC and platelets, increased transfusion requirement and decline in performance status and increase in symptoms.
 d. Certain targeted therapies may cause a differentiation syndrome, that is, a transient increase in the percentage of BM blasts (myeloblasts) and an absolute increase in PBs; in the setting of therapy with such compounds, an increase in blasts may not necessarily indicate PD.

Abbreviations: AML, acute myeloid leukemia, ANC, Absolute Neutrophil Count; BL, EMD, Extramedullary Disease; IWG, International Working Group, PB, Peripheral Blood Blast; WBC, White Blood Cell.

References

BGBC003 v10.0 (US);

Appendix 6: International Working Group Response Criteria in Myelodysplastic Syndromes (Cheson, 2006)

Category A: Altering the natural history of disease			
IWG Response Criteria in MDS	Bone Marrow ^a	Peripheral Blood ^a	Additional Considerations
Complete Remission (CR)	≤5% myeloblasts with normal maturation of all cell lines with no evidence for dysplasia ^b	Normalization of blood counts as defined by: 
 • Hb ≥11g/dL (not supported by EPO or transfusions) • Platelets ≥100 x 10⁹/L or 100,000/µL (not supported by transfusions) • Neutrophils ≥1.5 x 10⁹/L or 1,500/µL (not supported by G-CSF) • PB 0% 	Responses to be confirmed in two successive assessments; response parameters in peripheral blood needs to be maintained for at least 6 weeks.

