## 4.6 Withdrawn Subjects

Patients may withdraw informed consent and discontinue from the study at any time, or for any reason, without prejudice to their future treatment. In addition, a patient must be discontinued from the study if any of the following criteria are met:

- Patient non-compliance with the protocol, as agreed by the investigator and the sponsor
- Patient lost to follow-up
- Termination of the study by the sponsor
- Patient experiences an unacceptable toxicity that precludes them from continuing in the study e.g. patient experiences a ventricular arrhythmia (see study protocol Section 12.2), as agreed by the investigator and the sponsor

- Lack of adequate recovery from a DLT, see Section 9.2.1.2 in study protocol
- Failure of toxicity to adequately resolve, as outlined in Section 12.2 in study protocol
- Female patient becomes pregnant
- Patient experiences clinical disease progression
- Patient and/or investigator decision

AEs resulting in discontinuation will be followed as outlined in study protocol Section 9.3.4.

Patients who discontinue during the DLT assessment period (Part A), for any reason other than a DLT, will be replaced. All other patients who discontinue study treatment will not be replaced.

If a patient discontinues treatment prior to study completion, and for reasons other than progression or non-tolerability, every effort should be made to conduct the Final Study Visit assessments as outlined in Section 11.5 of the protocol. The reason for the patient's withdrawal from the study must be recorded in the eCRF.

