## Relapse Free Survival [RFS]

Relapse free survival [RFS]: defined as the months from the date of response until the date of relapse as confirmed by blast counts assessment (date of the disease progression will be used since disease progression is based in blast count assessment) .

Relapse Free Survival is defined only for subjects with a best objective response of CR/CRI/CRp/PR for AML patients or CR, PR, MR, PMR for MDS patients. Subjects who do not achieve CR/CRI/CRp/PR will be excluded from this analysis.

Duration of RFS is calculated as (days):

- Date of disease relapse, patient death, or censoring - Date of first Response evaluation + 1.
- Subjects without an objective disease relapse who die for any reason will be considered to have an event on the date of death. Otherwise subjects will be censored at the date of last objective response assessment showing no relapse has occurred.

Reason for censoring	Rule
Early death	Date of death
Disease progression leading to discontinuation	Date of last OR with no relapse
New anticancer treatment started before documentation of disease progression or death	Date of last radiological assessment prior to the start of non-protocol anticancer treatment

RFS will be summarized with (Mean (SD), median, min and max).

RFS will be presented graphically using Kaplan-Meier method.

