## 6.7 Appendix

### 6.7.1 Definitions of End Points for Clinical Trials in AML by Cheson & all 2003.

Outcome	Response Category	Point of Measurement	Definition
Overall survival	All patients	Entry onto trial	Death from any cause
Relapse-free survival	CR	Leukemia-free state	Disease relapse or patient death from any cause
NOTE. Complete blood counts should be evaluated at least monthly, or more often if clinically indicated, to establish the durability of responses.			
Abbreviations: AML, acute myelogenous leukemia; CR, complete remission.

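### SAP 5.7 gives conflicting rules on whether progression and early death end or censor RFS, uses radiology dates for censoring in a blood-and-marrow trial, and plans mean (SD) summaries of censored RFS and EFS times

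*SAP*

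**What the plan says.** **RFS events.** The definition in SAP 5.7 runs to the "date of relapse as confirmed by blast counts assessment", and adds that the "date of the disease progression will be used since disease progression is based in blast count assessment". On death it says: "Subjects without an objective disease relapse who die for any reason will be considered to have an event on the date of death". SAP Appendix 6.7.1 agrees, giving the RFS event as "Disease relapse or patient death from any cause".

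**RFS censoring.** The table that follows is headed as a list of reasons for censoring and has no outcome column. Its rows are early death (dated at death), "Disease progression leading to discontinuation" (dated at the last response without relapse), and new anticancer treatment (dated at the last radiological assessment before that treatment).

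**EFS censoring.** The event is death or progression. Both censoring rows, new anticancer treatment and alive without progression, use a radiological assessment date.

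**Summaries.** RFS and EFS each get mean (SD), median, minimum and maximum in the table, and a KM figure. OS gets KM estimates with a 95% CI for the median. The table titles in SAP 6.3.2 repeat the contrast: RFS and EFS are summaries, OS is a KM analysis.

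**The concern.** Two programmers working from the same section could build different RFS datasets. One would count progression that ends treatment as a relapse. The other would censor it at the previous clean assessment.

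The second choice is informative censoring: the patients removed are exactly those who have just relapsed, so RFS is lengthened. In an open-label single-arm study, an event rule left open until the data are visible is also hard to defend.

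The radiology dates leave the EFS rules without a usable date for any censored patient. A mean of partly censored durations underestimates the true mean, so the tables could disagree with the KM figures for the same endpoint.

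**Working it through.** There is no plan figure to reproduce, so the first step is to compare the texts.

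**1. Progression row: two readings.**
- *Narrow*: it covers only progression without blast confirmation. In support, the definition requires blast confirmation, and SAP 4.6 lists "Patient experiences clinical disease progression" among the reasons for discontinuation.
- *Literal*: it covers all progression that ends treatment. In support, the same RFS paragraph says progression is itself blast-based, and protocol 12.5 requires discontinuation when "Patient experiences PD (unless in the opinion of the investigator, they continue to derive clinical benefit" and continuation is agreed.

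The SAP does not say which applies. Protocol Appendix 5 also counts "New EMD disease" as progression. That is not a blast count, and the SAP gives no rule for it.

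**2. Early death row.** The date is the date of death under both text and table, so only the event flag is in doubt. The only other use of the term, in SAP 5.8.1.1, means death within 4 weeks of Cycle 1 Day 1. The first response assessment is at Cycle 2 Day 1, so under that meaning few responders could be affected.

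**3. Radiology.** Protocol 13.4 assesses response by blasts in blood and marrow, neutrophils, platelets and transfusion need. Protocol Tables 4 to 6 schedule no imaging except echocardiogram/MUGA. The RFS default (last objective response assessment) is sound. EFS has no such default.

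**4. Size of the progression row.** All inputs are assumed, since the documents give none: exponential RFS with true median 6 months, 20% of events deaths without relapse, follow-up uniform over 3 to 24 months, visits every 63 days (3 cycles of 21 days). Let *f* be the share of relapses recoded as censored.

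With exact dates and no back-dating, the event hazard falls by the factor 1 − 0.8*f*. Then:
- KM median = 6 / (1 − 0.8*f*)
- 12-month RFS = 2^(−2(1 − 0.8*f*))

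A simulation of 400,000 patients per scenario adds the visit grid. Relapse is dated at the detecting visit, recoded relapses go back to the previous visit, deaths are exact, and 29% of patients are censored under the text rule.

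| *f* | 1 − 0.8*f* (events kept) | Formula: median, 12-month RFS | Simulated: median, 12-month RFS |
|---|---|---|---|
| 0 (text rule) | 100% | 6.0, 25% | 6.2, 29% |
| 10% | 92% | 6.5, 28% | 7.1, 31% |
| 25% | 80% | 7.5, 33% | 8.3, 36% |
| 50% | 60% | 10.0, 44% | 10.4, 45% |
| 80% | 36% | 16.7, 61% | 15.1, 59% |

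Simulated medians move in visit steps, so 12-month RFS is the steadier measure. The 10% row stands in for the narrow reading. Sensitivity at *f* = 50%:
- Death share 30% to 10%: median 9.2 to 10.4, against 6.2 under the text rule.
- True median 4 months: 6.2 against 4.1.
- True median 9 months: 14.5 against 10.4.

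**5. Small cohorts.** At the design ORR of 20%, expected responders are 14 × 0.20 = 2.8 or 20 × 0.20 = 4. With 3 or 4 responders and *f* = 50%, at least one relapse is recoded in about 63% or 73% of trials. The KM median is then not reached in about 35% or 30%, against 13% or 6% under the text rule. At *f* = 25% it is not reached in about 22% or 16%.

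**6. Raw summaries.** In the base case the raw mean is about 6.65 months against 9.5 without censoring, and 1 − 6.65/9.5 = 30% low. Across scenarios it is 19% to 43% low. The raw median depends on the visit grid: 6.2 against a KM median of 6.2 with 63-day visits, but 5.1 against 6.0 with exact dates.

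**The case against.** The best defence is that the literal reading cannot be intended. If all progression ending treatment were censored, the sentence making the progression date the relapse date would have little left to govern. The protocol also says, in 9.3.2.1 and 12.5, that dosing beyond progression does not alter the progression date for analysis. The main text and the appendix give a workable rule, and the table is then a badly drafted supplement. On the narrow reading the effect is small: 12-month RFS goes from 29% to 31% in the illustration.

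Further points for the plan:
- Efficacy is declared exploratory in protocol 16.5.2.
- Patient-level RFS, EFS and response listings are planned, so any recoding would be visible.
- The radiology wording looks like a carry-over.
- KM figures are planned for both endpoints, the PROC LIFETEST code in SAP 5.15 is not limited to OS, and the table shells are a separate document not available here.
- Response criteria are reviewed more often than every 63 days in some cohorts.

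Much of this stands. The narrow reading is the more plausible one, the early-death row matters little, and no firm claim can be made about the raw median. But nothing in the table limits the progression row to unconfirmed cases, a listing shows a coding choice without settling it, and a mean (SD) is not a KM summary whatever the shells say. One limit on the radiology point: only the US protocol v10.0 was available, whereas the SAP cites US v9.0 and three other national protocols.

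**Conclusion.** The concern holds. SAP 5.7 contradicts itself on RFS events, names censoring dates that the available protocol does not schedule, and specifies a mean that is biased low whenever anyone is censored. These are errors in stated rules, not missing detail.

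The direction of the RFS bias is upward on either reading of the progression row. Its size is uncertain because the share of relapses affected is unknown: small if about 10% are recoded, large if half or more are. All magnitudes rest on the assumed inputs above.

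The consequences are confined to the reporting of RFS and EFS. It should be fixed before database lock.

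**What to change.** - State that relapse/progression or death from any cause is always an RFS event, and delete the early-death row.
- Delete the progression row, or limit it explicitly to progression not confirmed by blast assessment. If it is kept, say whether new extramedullary disease counts as confirmed, and add a sensitivity analysis counting the censored cases as events.
- In both censoring tables, replace the radiology date with the date of the last bone marrow or peripheral blood response assessment.
- Censor EFS at Day 1 when no post-baseline assessment precedes new anticancer therapy. SAP 4.5.3 requires such an assessment but not that it come first, and protocol Tables 5 and 6 also mark response assessment at End of Study and Follow-Up.
- Tabulate RFS and EFS as OS is tabulated (events, censored, KM median with 95% CI) and drop mean (SD).

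The cost is SAP wording and two table shells, using the PROC LIFETEST code already in SAP 5.15, plus one optional sensitivity run. No new data are needed.

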### Event Free Survival [EFS]

Event is defined as death or progression.

Duration of EFS is calculated as (days):

- Date of onset of Event, patient death or censoring - Date of first intake of study treatment (BGB324) + 1.

Situation	Date of Progression or Censoring	Outcome
New anticancer treatment started before documentation of disease progression or death	Date of last radiological assessment prior to the start of non-protocol anticancer treatment	Censored
Alive and without documentation of disease progression	Date of last radiological assessment	Censored

EFS will be summarized with (Mean (SD), median, min and max).

EFS will be presented graphically using Kaplan-Meier method.

### Overall Survival [OS]:

OS is defined as the months from the first day of treatment until date of death for any cause. Patients who were alive at the time of the final analysis will be censored at the date the patients was known to be alive.

Patient who do not die during the study will be followed up until date of death collected in the Survival Follow up CRF form or will be censored with the last Date of Follow-up when the patient was still alive.

Date of last known to be alive is the last date with available information for a subject in the study.

Duration of OS is calculated as (days):

- Date of death or censoring (date of last known to be alive) - Date of first intake of study treatment (BGB324) + 1.

OS will be summarized using Kaplan-Meier estimates (number of subjects who died, number of subjects censored, min, max, median, 95%CI of median).

## 5.8 Safety Analysis

No formal statistical analysis will be performed. The safety endpoints will consist of treatment-emergent adverse events, physical examinations, vital signs, ECOG, ECG, Echocardiograms, and laboratory tests (clinical chemistry, hematology and urinalysis). Change from baseline will be presented where appropriate.

### 5.8.1 Adverse events

The number and percentage of patients reporting TEAEs will be tabulated by MedDRA preferred term and system organ class, and summarized by CTCAE grade also. All AEs commencing prior to dosing with study medication will be excluded from the tabulation but will be fully listed.

A subject with more than one occurrence of the same adverse event in a particular system organ class will be counted only once in the total of those experiencing adverse events in that particular system organ class. If a subject experiences the same adverse event at more than one severity, or with more than one relationship to study drug, the most severe rating or the stronger causal relationship to study drug will be given precedence. Any missing severity, causality, or outcome will not be imputed and classed as unknown.

An overall summary classifying subjects with events according to seriousness, severity, maximum relationship to BGB324, and maximum CTCAE grade will also be presented.

Related events are defined as events that are definitely, possibly or probably related to study medication or with an unknown relationship.

Treatment-Emergent AEs are any AEs that start or worsen after first dose of study drug until 28 days following the last dose. AEs with partial onset dates will be assumed to have the latest possible onset date (while accounting for stop date) for determining treatment emergence, but no formal imputation will be done. AEs that have missing onset dates will be considered to be treatment-emergent, unless the stop date is known to be prior to the first administration of BGB324.

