9.3.1. Screening

Patient eligibility for the study will be determined within 14 days prior to the first dose of study treatment. Screening assessments will be conducted according to the Schedule of Events tables in Section 11.

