13.1.1. Resting 12-lead ECG

For timing of individual measurements please refer to relevant Schedule of Events (Tables 4-6) in Section 11.

Twelve-lead ECGs will be obtained after the patient has rested in a supine position for $>$ 10 minutes in each case. All 12-lead ECGs should be recorded while the patient is in the supine position. The investigator or designated physician will review the paper copies of each of the timed 12-lead ECGs on each of the study days when they are collected. ECGs will be conducted in triplicate and performed $<$ 5 minutes apart.

ECGs will be recorded at 25 mm/sec. A clinically significant ECG finding must be recorded as part of the medical history, if observed prior to start of dosing, and as an AE post-dose, where the finding represents a change from baseline.

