15.1.1. Adverse Event

An AE is any untoward medical occurrence in a patient or clinical study subject administered a pharmaceutical product and which does not necessarily have a causal relationship with the product. An AE can therefore be any unfavorable or unintended sign, symptom or disease temporally associated with the use of the IMP whether or not considered related to the IMP. This includes any occurrence that is new, an exacerbation of an existing disease (a worsening of the character, frequency or severity of a known condition) or abnormal results of diagnostic procedures, including clinically significant laboratory test abnormalities.

Suggested criteria for the assessment of clinical significance for laboratory abnormalities are as follows.

The laboratory abnormality:

- is clearly consistent with the pattern of leukemia disease or progression;
- is accompanied by clinical symptoms;
- requires study drug dose modification or interruption or permanent discontinuation of study treatment;
- requires more frequent follow-up assessments, further diagnostic investigation, etc.;
- requires a change in concomitant medication, therapy, or treatment.

If the clinically significant laboratory abnormality is a sign of a disease or syndrome (e.g. alkaline phosphatase and bilirubin 5X ULN associated with cholecystitis), only the diagnosis (e.g. cholecystitis) needs to be recorded on the AE eCRF. If the clinically significant laboratory abnormality is not a sign of a disease or syndrome, the abnormality itself should be recorded as an AE or SAE on the eCRF. If the laboratory abnormality can be characterized by a precise clinical term, the clinical term should be recorded as the AE or SAE. For example, an elevated serum potassium level of 7.0 mEq/L should be recorded as "hyperkalemia." Observations of the same clinically significant laboratory abnormality from visit to visit should not be repeatedly

recorded as AEs or SAEs on the eCRF, unless their severity, seriousness, or etiology changes.

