For all AEs, a diagnosis should be recorded on the eCRF rather than individual signs and symptoms (e.g. record only liver failure or hepatitis rather than jaundice, asterixis, and elevated transaminases) wherever possible. However, if a constellation of signs and/or symptoms cannot be medically characterized as a single syndrome at the time of reporting, each individual sign and/or symptom should be recorded as an AE or SAE on the eCRF. If a diagnosis is subsequently established, the reported event term should be updated to reflect the medical diagnosis.

Note that AEs occurring secondary to an initiating event that are separated in time or medically significant should be recorded as independent events on the eCRF. For example, if a severe gastrointestinal hemorrhage leads to a renal failure, both events should be recorded separately on the eCRF.

A pre-existing medical condition which is present at the start of the study and described in the Medical History eCRF, should only be recorded as an AE or SAE if the frequency, severity, or character of the condition worsens during the study. When recording such events on the AE eCRF, it is important to convey the concept that the pre-existing condition has changed by including applicable descriptors (e.g. “more frequent headaches”).

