15.2. Monitoring and Reporting Events

15.2.1. Adverse Events

Any AE experienced by a patient between signing the informed consent form (ICF) and 28 days after the last administration of bemcentinib is to be recorded in the eCRF regardless of the severity and causality of the event, although only events considered to be related to treatment need to be recorded between the last administration of bemcentinib and the end of the 28-day follow up period. If bemcentinib-related toxicities continue beyond the Follow-up period, patients will be followed until all bemcentinib-related toxicities have resolved to Grade ≤1, stabilized or returned to baseline.

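### SAP 5.8.1 both includes and excludes an AE that begins before first dose and worsens on drug, and no rule says which sentence governs the tables

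*SAP*

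**What the plan says.** Three statements in SAP 5.8.1 (Adverse events) bear on the point.

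- What is tabulated: "The number and percentage of patients reporting TEAEs will be tabulated by MedDRA preferred term and system organ class".
- What is left out: "All AEs commencing prior to dosing with study medication will be excluded from the tabulation but will be fully listed".
- What a TEAE is: "Treatment-Emergent AEs are any AEs that start or worsen after first dose of study drug until 28 days following the last dose".

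Protocol 16.4.2 has the same exclusion, but no clause on worsening. SAP 5.14, which lists the changes from the protocol's planned analyses, does not mention the difference.

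Pre-dose AE records are foreseen. Protocol 15.2.1 sets the recording period as "Any AE experienced by a patient between signing the informed consent form (ICF) and 28 days after the last administration of bemcentinib". On the length of the pre-dose interval, protocol 9.3.1 says: "Patient eligibility for the study will be determined within 14 days prior to the first dose of study treatment".

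**The concern.** An AE that starts in screening and rises in grade on bemcentinib meets the TEAE definition. Its onset date also puts it under the exclusion. Two programmers working from the same section could build different tables, and both could cite the SAP.

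Safety and tolerability is the primary objective of Part B (protocol 8.1.1), and the analysis is descriptive (SAP 5.8), so the AE tables carry the result. The subset tables in SAP 5.8.1.1 (related, serious, Grade 3 or higher, leading to discontinuation) would take over whatever rule is used to select events. If the exclusion is followed, the effect runs one way: counts can fall but cannot rise.

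The section is also uneven. An AE with no onset date is treated as emergent unless it is known to have stopped before first dose. An AE with a known screening onset and documented worsening on drug is barred if the exclusion is read literally.

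**Working it through.** The plan states no figure to reproduce. The check sets the rules side by side and then works out the weight of one patient.

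**Step 1: apply both rules to each type of event (SAP 5.8.1).**

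| AE | TEAE definition | Exclusion sentence | Conflict |
|---|---|---|---|
| Starts after first dose | Counted | Not excluded | No |
| Starts before first dose, does not worsen | Not counted | Excluded | No |
| Starts before first dose, worsens after it, with a new post-dose record | Counted | New record not excluded | No |
| Starts before first dose, worsens after it, on one record with the original onset | Counted | Excluded | Yes |

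Only the last row is in dispute.

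**Step 2: can that row occur?** Recording starts at consent (protocol 15.2.1), and eligibility is determined within the 14 days before first dose (protocol 9.3.1). Protocol 15.3.1 asks for the highest grade since the last visit. It does not tell sites to open a new record with a new onset date when the grade rises. A screening AE can therefore keep its pre-dose onset and carry a post-dose grade.

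**Step 3: which worsened findings already get an AE after dosing?**

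- Medical-history conditions: such a condition "should only be recorded as an AE or SAE if the frequency, severity, or character of the condition worsens during the study" (protocol 15.1.1).
- Clinically significant laboratory abnormalities: repeat observations are not to be "recorded as AEs or SAEs on the eCRF, unless their severity, seriousness, or etiology changes" (protocol 15.1.1).
- ECG findings: a clinically significant finding goes into the medical history "if observed prior to start of dosing, and as an AE post-dose, where the finding represents a change from baseline" (protocol 13.1.1).
- Spontaneously reported symptoms: recorded as an AE when new or changed from baseline (protocol 13.1.4).
- Physical examination and echocardiogram: new or worsened post-baseline findings are recorded as AEs (SAP 5.8.2 and 5.8.6).

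These rules may give the event a post-dose onset, which moves it to the third row of the table. For other AEs first recorded between consent and first dose, no rule requires a new record on worsening.

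**Step 4: weight of one patient.** The inputs are the planned maximum evaluable sizes: 14 for each of B1 to B4 and 20 for B5 (protocol 9.2.2 and 16.9). SAP 5.1 also summarizes AE data for B2 and B5 together.

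- Cohort of 14: 1/14 = 7.1 percentage points.
- Cohort of 20: 1/20 = 5.0 points.
- B2 and B5 combined: 14 + 20 = 34, and 1/34 = 2.9 points.

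These are illustrations. The actual denominator is the safety population (SAP 4.5.2 and 5.1), which need not equal the evaluable number.

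**The case against.** The strongest reply is that nothing is shown to be lost. SAP 5.8.1 says that TEAEs are what is tabulated and then defines them to include worsening, so a programmer who derives a TEAE flag from the definition keeps the event. This stands as far as it goes. A reader might infer from the exclusion sentence that these events are certain to drop out of the tables, and the documents do not support that. They support an unresolved contradiction, with a loss only if the exclusion is the sentence that is followed.

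The second reply is that few records are exposed. The recording rules in Step 3 cover many worsened findings, and worsening cytopenia is also shown in the hematology CTCAE shift tables (SAP 5.8.7). The AE rows of all three Schedules of Events (protocol Tables 4 to 6) are blank at screening, and the screening procedures in protocol 11.2 do not include AE recording. Routine SAE reporting starts at first dose (protocol 15.2.2). This also stands. It reduces the number of affected records but does not reconcile the two sentences, and protocol 15.2.1 still starts recording at consent.

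Third, safety is descriptive and the excluded events remain fully listed. That limits the harm to the tables. It does not remove the harm, because the tables are what readers will use for incidence.

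**Conclusion.** The two sentences in SAP 5.8.1 cannot both be applied to an AE that starts between consent and first dose and worsens on drug, and neither document says which prevails. If the exclusion is applied as written, TEAE, related and Grade 3 or higher counts can only be understated. The number of affected events is unknown and probably small.

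The only firm size is the weight of one patient: 7.1, 5.0 or 2.9 points on a preferred-term row, at planned sizes. The row for any TEAE moves only if the patient has no other TEAE.

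A reader might go further and infer a double-digit loss. Suppose that 20 to 40% of patients have an AE open at first dose and that half of these worsen. In a cohort of 14 that is 14 × 0.20 × 0.5 = 1.4 to 14 × 0.40 × 0.5 = 2.8 patients, or 10 to 20 points. The documents give neither proportion. The arithmetic also ignores the recording rules above, and a single row would move that far only if every affected patient shared it. That estimate should not be used.

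This is worth correcting because it concerns the primary safety tables and the remedy is small.

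**What to change.** In SAP 5.8.1, limit the exclusion to AEs that start before first dose and do not worsen on or after first dose, and keep the provision that excluded events are listed in full. Identify worsening by a post-dose CTCAE grade above the last pre-dose grade, and tabulate the event at its post-dose grade. A rise in grade is enough to make the TEAE definition workable; no further criterion, such as becoming serious, is needed.

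Align protocol 16.4.2 with the revised sentence, or record the change in SAP 5.14.

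The cost is one sentence and one derivation flag. Reported AE rates may rise slightly.
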